Effect of guided imagery for radiotherapy-related distress: A randomized controlled trial for patients with head and neck cancer.

Protocol Number: 18-1100

Principal Investigator: [name]
[name]
[name],
[name]
[contact]

**Coordinating Center
and Co-Investigators:** The University of Colorado
Anschutz Medical Campus
[name]
[name]

Funded by: University of Colorado American Cancer Society
Institutional Research Grants
University of Colorado Cancer Center Investigator
Initiated Trials Program (regulatory support)

Version Date: 03/30/2021

**PI: [name]
Protocol #: 18-1100
Version Date: 30MAR2021**

STATEMENT OF COMPLIANCE

This is an investigator-initiated study. The principal investigator (PI), [name], is conducting the study and acting as the sponsor. As the sponsor-investigator, both the legal/ethical obligations of a PI and those of a sponsor will be followed.

The trial will be carried out in accordance with Good Clinical Practice (GCP) as required by applicable United States (US) laws and applications, including but not limited to United States (US) Code of Federal Regulations (CFR) applicable to clinical studies (45 CFR Part 46).

The PI will assure that no changes to the protocol will take place without documented approval from the Institutional Review Board (IRB). All personnel involved in the conduct of this study have completed Human Subjects Protection Training.

I agree to ensure that all staff members involved in the conduct of this study are informed about their obligations in meeting the above commitments.

Sponsor-Lead Principal Investigator: [name]
Print/Type Name

Signed: _____

Date: _____

LIST OF ABBREVIATIONS

ACRONYM	DESCRIPTION
GI	Guided imagery
HNC	Head and neck cancer
IIT	Investigator-Initiated Trial
RT	Radiotherapy
TLFB	Time line follow-back

PROTOCOL SUMMARY / SYNOPSIS

Protocol Title:

Effect of guided imagery for radiotherapy-related distress: A randomized controlled trial for patients with head and neck cancer.

Objectives:

- **Primary Objective:**
Evaluate the feasibility and acceptability of the guided imagery intervention to reduce RT-related symptoms of anxiety and depression in patients with HNC. These data will be used to inform future grant applications.

- **Secondary Objectives:**
We will also collect data to evaluate the impact of a GI intervention on symptoms of anxiety and depression in patients with HNC relative to treatment as usual.

Endpoint:

- **Primary Endpoint:**
Acceptability and feasibility of guided imagery intervention assessed through self-reported intervention use and qualitative interviews with intervention participants
- **Secondary Endpoints:**
Self-reported anxiety and depression at one month after completion of radiotherapy as measured by the Hospital Anxiety and Depression Scale
- **Tertiary/exploratory:**
Self-reported use of anxiolytic medications as measured by timeline follow-back methodology. We will also measure health-related quality of life in patients receiving the intervention and treatment as usual.

Population:

- **Sample size**
 - Maximum number of participants that can be enrolled is 72 (allow for screen failures)
 - Minimum number of participants to be enrolled 50 (number of participants needed to answer scientific question/aims)
- **Gender** Male and Female
- **Age Range** 18-100
- **Demographic group** Ambulatory outpatients receiving radiotherapy for head and neck cancer

- **General health status** Initiating radiotherapy for head and neck cancer

Number of Participating Sites enrolling participants:

[figure not shown]
1 (University of Colorado Cancer Center)

Description of Study

Agent: Guided imagery

Study Duration: 2 years

SCHEMATIC OF STUDY DESIGN

1 PARTICIPATING SITES

A complete and current listing of investigators, research personnel, research facilities and other study centers (if applicable) participating in this study will be maintained throughout the duration of this study.

2 INTRODUCTION: BACKGROUND INFORMATION AND SCIENTIFIC RATIONALE

2.1 BACKGROUND INFORMATION

Patients with head and neck cancer (HNC) comprise a unique population due to their high risk for treatment failure and death [1, 2], heavy symptom burden [3], and intensive treatment schedules. As a result, HNC has been labeled the “most psychologically traumatic cancer to experience.” ([4], p 2) These patients are at risk for facial disfigurement and functional changes in ability to speak, breathe, eat and swallow [4-7]. As compared to patients with other cancer diagnoses, patients with HNC report high levels of psychological distress (i.e., symptoms of anxiety and depression) and social isolation [8-12], with more than half of HNC patients reporting persistent psychological distress [13]. Additionally, their risk for suicide is four times that of the general population [14]. Evidence shows that much of their distress is directly related to the treatments they undergo, including radiotherapy (RT;[8]). This is an at-risk, high needs population of cancer patients in need of an intervention for treatment-related distress.

Radiotherapy (RT), a standard treatment for head and neck cancer, is associated with high levels of psychological distress in HNC patients [8, 15]. RT involves daily treatments often for weeks at a time. Treatment begins with a “CT simulation” to determine accurate positioning while undergoing RT [16]. Prior to initiating RT, rates of clinically significant anxiety range from 20% to 47%, depending on assessment measure, and initially peak around week five of RT [8, 17-19]. Pretreatment depression tends to be lower than anxiety (15%), but increases over the course of treatment (29%) and persists post-RT [18, 20, 21].

Head and neck cancer is highly prevalent with approximately 650,000 cases diagnosed each year [22], and yet it is understudied in the field of behavioral medicine [4]. This is surprising given the high levels of psychological distress [23] which can complicate adjustment to diagnosis and treatment [6], as well as overall survival [24]. Psychological distress is a significant predictor of patient survival [25] with lower survival rates shown for cancer patients who reporting symptoms of depression (71% versus 86%) [17]. For HNC patients undergoing RT specifically, levels of depression have been associated with decreased overall survival [15]. It is critical that

these difficulties be addressed given the direct relationships found between mental health and clinical outcome.

Guided imagery (GI) is a behavioral relaxation technique involving the visualization of calming images and is considered an adjuvant cancer therapy [26]. A systematic review of GI in a heterogeneous sample of patients with cancer found positive effects on depression, anxiety and quality of life compared to patients in a control group [26]. It has been found to enhance comfort and quality of life and reduce anxiety and fatigue in women undergoing RT for breast cancer [27]. The impact of GI in patients with HNC, a highly distressed population, is unknown.

2.2 RATIONALE

Patients with head and neck cancer (HNC) comprise a unique population due to their high risk for treatment failure and death [1, 2], heavy symptom burden [3], and intensive treatment schedules. Psychological distress is a significant predictor of patient survival [25] with lower survival rates shown for cancer patients who reporting symptoms of depression (71% versus 86%) [17]. For HNC patients undergoing RT specifically, levels of depression have been associated with decreased overall survival [15]. It is critical that these difficulties be addressed given the direct relationships found between mental health and clinical outcome. The goal of this interdisciplinary pilot study is to evaluate the feasibility, acceptability and preliminary efficacy of a guided imagery intervention to reduce RT-related symptoms of anxiety and depression in patients with HNC relative to treatment as usual. The findings will be used for future grant applications to perform larger studies.

Aim 1: To assess participants' perceived acceptance and feasibility of a guided imagery intervention for radiotherapy-related (RT) anxiety and depression in head and neck cancer patients through quantitative and qualitative data collection Head and neck cancer patients receiving RT (n = 72) will be randomly assigned to a guided imagery intervention for RT-related anxiety and depression or to treatment as usual. The intervention consists of two individual, in-person or virtual (telephone or videoconference), tailored sessions that will introduce a relaxation practice prior to CT simulation and during the first week of RT, as well as identification of integration strategies into the patients' treatment plans. The treatment as usual condition involved education about treatment and access to psychosocial support available through UCCC. Semi-structured interviews with participants from the intervention arm will assess the perceived acceptance and feasibility of guided imagery for addressing symptoms of anxiety and depression related to RT. Participants will track weekly use of the guided imagery intervention during RT via time line follow-back (TLFB) methods. We hypothesize that themes will emerge from the qualitative data that will indicate general acceptance and usefulness of guided imagery.

Aim 2: Determine the impact of a guided imagery intervention for radiotherapy-related (RT) anxiety and depression in head and neck cancer patients.

We hypothesize that guided imagery will result in measured decreases in patient reported anxiety and depression as measured by the Hospital Anxiety and Depression Scale over the course of RT. Additionally, we hypothesize that guided imagery will demonstrate greater reductions in

anxiety as compared to treatment as usual. We hypothesize that symptoms of depression will remain stable, rather than increasing, over the course of RT in participants in the guided imagery arm.

Exploratory Aim 1: To engage in exploratory analyses to investigate the potential impact of guided imagery on self-reported anxiolytic use. Anxiolytic use will be assessed via participant self-report using time line follow-back methods for weekly monitoring and data regarding prescription of anxiolytic drugs in the patient's electronic medical record. We expect that participants in the guided imagery group will report lower proportions of anxiolytic utilization than the control group.

Exploratory Aim 2: To examine the impact of a guided imagery intervention on health-related quality of life and perceived symptom burden compared to treatment as usual.

Participant-reported health-related quality of life and perceived symptom burden assessed by the Functional Assessment of Cancer Therapy - Head and Neck Version (FACT-HN) and symptom burden will be assessed by the Memorial Symptom Assessment Scale Short Form (MSAS-SF). We hypothesize that participants who receive the intervention will have higher health-related quality of life than participants who receive treatment as usual. We also hypothesize that symptom bother will be lower in participants who receive the guided imagery intervention compared to treatment as usual.

The successful implementation of this interdisciplinary research will result in lower psychological distress through the reduction of symptoms of anxiety and depression. This is particularly significant in a population of patients who are highly vulnerable to anxiety and depression as they undergo burdensome treatment and cope with heavy symptom burden. These psychological symptoms can influence treatment adherence and survival; thus, behavioral intervention is paramount. Guided imagery holds the potential to significantly improve distressing psychological symptoms in vulnerable patients facing intensive treatment and heavy symptom burden. This intervention will directly address psychological distress to establish preliminary efficacy that will lay the groundwork for larger efficacy and dissemination trials.

2.3 POTENTIAL RISKS AND BENEFITS

There are minimal risks to study participants. However, we will ask participants to complete measures assessing symptoms of anxiety, depression, quality of life, and symptom burden. In the case that this is upsetting, psychosocial support will be available. However, participants, particularly those who participate in the GI intervention, are expected to benefit from study participation. All participants in the study will ultimately receive the GI intervention materials. Further, the successful completion of this study will provide preliminary information about an intervention to reduce psychological distress in a vulnerable population. We strongly believe that the potential benefits of this study outweigh the risks.

2.3.1 KNOWN POTENTIAL RISKS

There are minimal risks to study participation. Participants will be asked to reflect on psychological states, which can be upsetting. All participants will have access to supportive oncology services available at the University of Colorado Cancer Center, including access to clinical psychologists and oncology social workers. All PHI will be protected by storing data in restricted access databases (REDCap).

2.3.2 KNOWN POTENTIAL BENEFITS

The risks to participants are reasonable in relation to the anticipated benefits to participants and/or society, and in relation to the importance of the knowledge that may reasonably be expected to result, thereby falling in favor of performing the study:

- To Participant: Guided imagery has been helpful in reducing the severity of symptoms of anxiety and depression in patients with cancer. Therefore, we expect that the participants in our study who are randomized to the intervention condition will experience lower levels of anxiety and depressive symptomology versus participants in the treatment as usual condition.
- To Society: This is a novel clinical project with the potential for wide-ranging impact. Head and neck cancer has been labeled the “most psychologically traumatic cancer to experience.” Depression and anxiety are highly prevalent in this population and can be exacerbated by cancer-directed treatment. Symptoms of depression affect immunocompetence, treatment adherence, and other aspects of health-related quality of life that persist after the treatment completion. Patients with anxiety report a greater impact of their disease including intrusive thoughts and avoidance behaviors. Yet, there is a paucity of well-designed randomized controlled trials targeting psychological distress in this population.
- Justify the importance of the knowledge gained: There are no published interventions of GI for anxiety and depression in patients with head and neck cancer despite its efficacy in other populations of patients with cancer. The goal of this intervention is ultimately to design an intervention that can be integrated into clinical care for patients with head and neck cancer.

3 OBJECTIVES AND PURPOSE

Primary objective: The goal of this interdisciplinary pilot study is to collect data to evaluate the feasibility and acceptability of the guided imagery intervention to reduce RT-related symptoms of anxiety and depression in patients with HNC. These data will be used to inform larger studies and grant applications.

Secondary objective: This study will also assess the impact of the GI intervention on symptoms of anxiety and depression in patients with HNC relative to treatment as usual

4 STUDY DESIGN AND ENDPOINTS

4.1 DESCRIPTION OF THE STUDY DESIGN

This will be a randomized controlled trial. Following consent, participants will provide baseline data including demographic and clinical characteristics. Participants will be randomized to the guided imagery intervention (delivered in-person or virtually) or to treatment as usual. Due to study design, it is not possible to blind either participants or investigators to study condition. However, the biostatistician will be blinded to participant group to minimize bias in analyzing the data. Participants will complete assessments at baseline, following initiation of RT, halfway through RT, at the end of RT, and one month after the end of RT.

4.2 STUDY ENDPOINTS

4.2.1 PRIMARY ENDPOINT

The primary endpoint of the study is the feasibility and acceptability of the guided imagery intervention for anxiety and depression related to radiotherapy. Feasibility and acceptability will be assessed following study participation through both qualitative and quantitative methods. Feasibility of intervention use will be assessed through rates of study enrollment and GI session attendance. It will also be assessed through self-reported use of the GI intervention measured through timeline follow-back. Acceptability of the intervention will be assessed through qualitative interviews with intervention participants. The interviews will assess participant experience in the intervention including thoughts about the intervention content and structure of the intervention.

4.2.2 SECONDARY ENDPOINTS

Self-reported anxiety and depression at one month after completion of RT are the secondary endpoints. This will be assessed by the Hospital Anxiety and Depression Scale. The Hospital Anxiety and Depression Scale (HADS; [28]) is a 14-item self-report measure of anxiety and depression symptoms for use in medically ill patients, as it does not include the somatic symptoms of anxiety and depression that confound the assessment of distress in medically ill patients, and has demonstrated high reliability and validity in medically ill populations [29]. The measure contains seven anxiety items and seven depression items, which correspond to two subscales (HADS-A and HADS-D). For each item, the participant is asked to identify how much a given statement is applicable (*Most of the time, A lot of the time, From time to time, Occasionally or Not at all*). A cut score of 8 identifies cases of anxiety and depressive disorders for each subscale, resulting in sensitivity and specificity of approximately .80 [29].

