7 STUDY PROCEDURES AND SCHEDULE

7.1 STUDY PROCEDURES/EVALUATIONS

Following consent and completion of baseline measures, the participant will be randomized to either the intervention or treatment as usual condition. The research study assistant will coordinate the scheduling of the two intervention sessions for participants in the GI condition. Administration of the study measures will occur online, via REDCap. Participants will be offered the opportunity to begin/complete the survey at the cancer center on a provided tablet, but may also complete the survey in its entirety at home on their own personal internet-connected device.

All participants will complete assessments at baseline, following initiation of RT (during Week 1 of treatment), approximately halfway through RT (during Week 3 of treatment), at the end of RT (during Week 7 of treatment), and one month following completion of RT (around Week 12 after beginning treatment). Patients may complete the assessments listed any time during the specified week (7 days) of treatment, with Day 1 being defined as the first day of radiation treatment. Each session will also be recorded and reviewed for fidelity to the intervention. Study measures include the following:

- I. Anxiety and depression

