10 STATISTICAL CONSIDERATIONS

10.1 STATISTICAL HYPOTHESES

- Primary Efficacy Endpoint(s):
Participants will find the intervention feasible and acceptable.
- Secondary Efficacy Endpoint(s):

(1) The HADS-A score will be smaller in patients receiving guided imagery intervention compared to controls (whose score should remain unchanged from baseline), and (2) the HADS-D score will be smaller in the guided imagery group compared to controls (whose HADS-D should increase over baseline)

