10.3.3 ANALYSIS OF THE SECONDARY ENDPOINT(S)

The study investigators will use independent sample t-tests at the end of radiation treatment (RT) to test the hypotheses (1) the HADS-A score will be smaller in patients receiving guided imagery intervention compared to controls (whose score should remain unchanged from baseline), and (2) the HADS-D score will be smaller in the guided imagery group compared to controls (whose

HADS-D should increase over baseline). The study is powered to test these hypotheses. Additionally, we will analyze the data using repeated measures analyses or mixed models to study changes over time and to test for interactions between time and treatment groups.

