10.4 SAMPLE SIZE

We expect that we will be able to enroll up to 72 patients who will be randomized into either control (n=36) or guided imagery intervention (n=36). Based on a published study looking at HADS scores in HNC patients receiving RT (20), we used the values for means and standard deviations (SD) from that study for our control group. We also determined that SD would be known and equal. Significance levels (alpha) are set at 0.05 for a two-sided independent-sample equal-variance t-test. For the HADS-A hypothesis, the mean score in controls at the end of RT was 6.9 (SD = 5.0). With group sample sizes of 36 and 36, we will have 80% power to reject the null hypothesis of equal means when the HADS-A score in the guided imagery group is ≤ 3.6 (a $\geq 48\%$ difference between the scores for each group at the end of RT). For the HADS-D hypothesis, the mean score in controls at the end of RT was 11.2 (SD=5.5). Group sample sizes of 36 and 36 achieve 80% power to reject the null hypothesis of equal means when HADS-D score in the guided imagery group is ≤ 7.5 (a $\geq 33\%$ difference between the scores at the end of RT). Although we can achieve reasonable power to detect clinically significant differences

between our study groups, the main goal of this study is to determine the feasibility of a larger study. As such, the results of our analyses are not meant to answer the question of the effectiveness of our intervention, but to provide preliminary data for a larger grant application.

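### The secondary HADS endpoint is declared at one month after radiotherapy (about Week 12), but its between-arm tests and power are set at the end of radiotherapy (Week 7)

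*Combined protocol and SAP*

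**What the plan says.** The Synopsis gives the secondary endpoint as "Self-reported anxiety and depression at one month after completion of radiotherapy as measured by the Hospital Anxiety and Depression Scale". Section 4.2.2 repeats it: "Self-reported anxiety and depression at one month after completion of RT are the secondary endpoints". Section 7.1 treats the end of RT and the one-month visit as two separate assessments: "at the end of RT (during Week 7 of treatment), and one month following completion of RT (around Week 12 after beginning treatment".

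The analysis sections use the other visit. Section 10.3.3, under the heading for the secondary endpoints, says: "The study investigators will use independent sample t-tests at the end of radiation treatment (RT) to test the hypotheses". It adds that the study is powered for those hypotheses. Section 10.4 takes its HADS-A inputs from the same visit ("the mean score in controls at the end of RT was 6.9 (SD = 5.0") and does likewise for HADS-D (control mean 11.2, SD 5.5).

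Two other places bear on the question without settling it. Section 10.1 states the hypotheses with no visit, for example "The HADS-A score will be smaller in patients receiving guided imagery intervention compared to controls". Aim 2 in section 2.2 expects decreases on the "Hospital Anxiety and Depression Scale over the course of RT".

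Section 10.3.3 also plans a longitudinal analysis: "we will analyze the data using repeated measures analyses or mixed models to study changes over time and to test for interactions". The interaction meant is that of visit with arm. The section does not list the visits in that model or name a contrast at any of them.

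**The concern.** A secondary endpoint should be tested at the visit at which it is defined. Here the endpoint definition points to one month after RT, while the test and power calculation point to the end of RT. These are different clinical questions: how patients feel as treatment finishes, and how they feel about five weeks later (Week 12 less Week 7).

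Two things follow. The stated power does not describe the declared endpoint. And each visit has support in the protocol as the secondary result, so the choice of which to report could be made after the data are seen. Section 4.1 says neither participants nor investigators are blinded. The biostatistician's blinding limits this risk but does not fix which visit is reported.

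The HADS results are not the primary purpose of the trial, but section 10.4 says the analyses are meant as preliminary data for a larger grant application. An effect estimate carried forward for that purpose needs a defined time point.

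**Working it through.** **Visits side by side**

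| Place | Visit for HADS |
|---|---|
| Synopsis, secondary endpoint | One month after RT |
| 4.2.2 | One month after RT |
| 2.2, Aim 2 | Over the course of RT |
| 7.1 | End of RT = Week 7; one month = around Week 12 |
| 10.1 | None named |
| 10.3.3, t-tests | End of RT |
| 10.3.3, longitudinal model | None listed |
| 10.4, means, SDs and power | End of RT |

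**Step 1. Reproduce the stated power.** Inputs from section 10.4: 36 per arm, two-sided alpha 0.05, equal-variance t-test. HADS-A is 6.9 against 3.6, SD 5.0. HADS-D is 11.2 against 7.5, SD 5.5.

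Noncentrality = difference / (SD × √(2/36)), with 70 degrees of freedom and critical value 1.994.

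- HADS-A: 3.3 / (5.0 × 0.2357) = 2.80. Power is 78.9% by the noncentral t, or 80.0% treating the SD as known, as section 10.4 does.
- HADS-D: 3.7 / (5.5 × 0.2357) = 2.85. Power is 80.4% by the noncentral t, or 81.4% with known SD.

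The stated 80% is therefore sound for the end of RT.

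**Step 2. Power at the declared visit.** The documents give no mean, SD or expected difference at one month, so this power cannot be computed. As an illustration only, keep the end-of-RT SDs and 36 per arm, and let a fraction of the end-of-RT difference be present at one month (noncentral t):

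| Effect at one month relative to end of RT | HADS-A difference | Power | HADS-D difference | Power |
|---|---|---|---|---|
| 125% | 4.13 | 93% | 4.63 | 94% |
| 100% | 3.30 | 79% | 3.70 | 80% |
| 75% | 2.48 | 54% | 2.78 | 56% |
| 50% | 1.65 | 28% | 1.85 | 29% |

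**Step 3. Effect of an open choice of visit on false positives.** This was simulated under no effect (2,000,000 draws), with each test two-sided at 0.05. The correlation between subscales and the correlation between visits are assumed equal, from 0.5 to 0.8. The correlation between different subscales at different visits is taken as the product of the two. None of these correlations is in the documents.

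| Assumed correlation | Two subscales, one visit | Two subscales, either visit | Increase (points) |
|---|---|---|---|
| 0.5 | 9.1% | 16.2% | 7.1 |
| 0.6 | 8.8% | 15.0% | 6.3 |
| 0.7 | 8.3% | 13.7% | 5.3 |
| 0.8 | 7.8% | 12.0% | 4.2 |

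Increases were taken before rounding. Only the last column is due to the visit. The 7.8–9.1% in the second column comes from testing two subscales and would remain after one visit is named.

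**Step 4. Does the longitudinal model fill the gap?** HADS is scheduled at baseline and Weeks 1, 3, 7 and 12, so the model could well include Week 12. But a time-by-treatment interaction asks whether the difference between arms changes across visits. It does not estimate or test the difference at one month. A model-based contrast at Week 12 would do so, and none is named.

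**The case against.** The strongest reply is that the analysis plan is not really open. Section 10.3.3 repeats the section 10.1 hypotheses, ties them to the end of RT and claims power for them, and section 10.4 uses the same visit. On this reading only the endpoint label is wrong, and a Week 12 t-test would be an unplanned addition. It is true that only one visit is named for the t-tests. But the label appears in both the Synopsis and section 4.2.2, and a reader checking a report against the declared endpoint would look for the one-month result. The mismatch stands.

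A second reply is that the longitudinal model would naturally use the Week 12 data. That is a fair reading, and it would be wrong to say those data go unused. What is missing is a named one-month contrast.

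Third, the false-positive figures are a worst case. They suppose that all four tests are run without adjustment and any one may be claimed, whereas the plan has two t-tests. If the cross-subscale, cross-visit correlation equals the other correlations instead of their product, the either-visit range is 11.4–15.6% and the increase is 3.6–6.5 points. Counting only false findings in favour of guided imagery, the increase is about 2.1–3.6 points under the product assumption. These points reduce the size but do not remove it. Likewise, the one-month power figures show sensitivity, not a demonstrated shortfall.

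Finally, this is a pilot. Its primary endpoint is feasibility and acceptability, section 10.4 disclaims any answer on effectiveness, and no decision rule depends on HADS. That limits the consequence and is why this is a correction that should be made, not a fundamental flaw.

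**Conclusion.** The concern holds. The current text declares the secondary HADS endpoint at one month after RT and tests and powers it at the end of RT, with no between-arm contrast named at the declared visit. This is a contradiction within the plan, not just missing detail.

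The contradiction rests on the text alone and needs no assumption. Its numerical consequences do rest on assumptions: the illustrative one-month power, anywhere from 28% to 94%, depends on carrying over the end-of-RT SDs and full numbers and on how much of the effect is present at one month. The 4 to 7 point rise in false-positive chance depends on the assumed correlations and on free choice between visits. The end-of-RT power claim itself is correct. The primary endpoint is untouched. The point should be fixed before results by arm are compared.

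**What to change.** Before any comparison of outcomes by arm, name one visit for the secondary HADS endpoint and use it in the Synopsis and in sections 4.2.2, 10.1, 10.3.3 and 10.4. The choice is the sponsor's. Either option resolves the contradiction:

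- **(a) End of RT.** Redefine the secondary endpoint as HADS-A and HADS-D at the end of RT, in line with the t-tests and the sample size section and broadly with Aim 2, whose wording describes a trajectory during RT. Keep one month as a named supportive contrast.
- **(b) One month after RT.** Keep the declared endpoint and make the Week 12 between-arm contrast the secondary analysis, either as a t-test or as an estimate from the planned mixed model with its visits listed. Label the end-of-RT t-tests supportive, and state in section 10.4 that the 80% power applies only to the end of RT.

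The cost is wording in those five places. HADS is already collected at Weeks 7 and 12, so no new data, visits or patients are needed. Naming one visit removes the part of the false-positive risk due to the visit. It does not address the two subscales each being tested at 0.05.
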